5.1 Primary Objective

- ✚ To demonstrate the bioequivalence of Metformin/Gliclazide fixed dose combination tablet (1000 mg /30 mg MR) compared with the co-administration of the individual tablets (Metformin 1000 mg XR and Gliclazide 30 mg MR), administered as single dose in fasting condition to healthy volunteers.
- ✚ To demonstrate the absence of an effect of Gliclazide on the PK of Metformin by comparing the Metformin PK following administration of the fixed combination tablet Metformin/Gliclazide and Metformin alone (AUC_{0-t} , $AUC_{0-\infty}$ and C_{max} of Metformin).
- ✚ To demonstrate the absence of an effect of Metformin on the PK of Gliclazide by comparing the Gliclazide PK following administration of the fixed combination tablet Metformin/Gliclazide and Gliclazide alone (AUC_{0-t} , $AUC_{0-\infty}$ and C_{max} of Gliclazide).

5.2 Secondary Objectives:

- ✚ To assess clinical safety and tolerability for all experimental treatments.

6 Statistical Hypothesis

1. Test bioequivalence of fixed combination and separate tablets

$H_0: \mu_T / \mu_R \leq 0.8$ or $1.25 \leq \mu_T / \mu_R$ for Metformin and/or Gliclazide AUC_{0-t} , $AUC_{0-\infty}$ or C_{max} ,
or for all

$H_1: 0.8 < \mu_T / \mu_R < 1.25$ for all Metformin and Gliclazide primary endpoints (i.e. AUC_{0-t} ,
 $AUC_{0-\infty}$ or C_{max})

μ_T and μ_R being the means under Test and Reference treatment, respectively.

Test treatment: Metformin/Gliclazide fixed dose combination tablet (1000 mg /30 mg MR).

Reference treatment: co-administration of the individual tablets (Metformin 1000 mg XR and Gliclazide 30 mg MR).

Bioequivalence is confirmed if all six 90% CIs for all six primary endpoints reside within the acceptance range [0.80 – 1.25].

2. Test absence of an effect of Gliclazide on the PK of Metformin

$H_0: \mu_T / \mu_R \leq 0.8$ or $1.25 \leq \mu_T / \mu_R$ for Metformin AUC_{0-t} , $AUC_{0-\infty}$ or C_{max} , or for all

$H_1: 0.8 < \mu_T / \mu_R < 1.25$ for all Metformin primary endpoints (i.e. AUC_{0-t} , $AUC_{0-\infty}$ or C_{max})

μ_T and μ_R being the means under Test and Reference treatment, respectively.

Test treatment: Metformin/Gliclazide fixed dose combination tablet (1000 mg /30 mg MR).

Reference treatment: Single administration of Metformin 1000 mg XR

Absence of an effect of Gliclazide on the PK of Metformin will be concluded, if all three 90% CIs for Metformin endpoints reside within the range [0.80 – 1.25]

3. Test absence of an effect of Metformin on the PK of Gliclazide

$H_0: \mu_T / \mu_R \leq 0.8$ or $1.25 \leq \mu_T / \mu_R$ for Gliclazide AUC_{0-t} , $AUC_{0-\infty}$ or C_{max} , or for all

$H_1: 0.8 < \mu_T / \mu_R < 1.25$ for all Gliclazide primary endpoints (i.e. AUC_{0-t} , $AUC_{0-\infty}$ or C_{max})

μ_T and μ_R being the means under Test and Reference treatment, respectively.

Test treatment: Metformin/Gliclazide fixed dose combination tablet (1000 mg /30 mg MR).

Reference treatment: single administration of Gliclazide 30 mg MR

Absence of an effect of Metformin on the PK of Gliclazide will be concluded, if all three 90% CIs for Gliclazide endpoints reside within the range [0.80 – 1.25]

7 Investigational Plan

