Objectives:	
Primary objectives
 
 • Demonstrate bioequivalence of the new fixed dose modified release combination for Metformin 1000 mg plus Gliclazide 30 mg MR compared to the concomitant administration of single tablets of Metformin 1000 mg XR and Gliclazide 30 mg MR. • Demonstrate the absence of drug interaction between the combination and the administration of each single tablet. 
Secondary objective is Clinical safety and tolerability will also be assessed.

Methodology:	A randomized, open label, single dose, 4 periods, 4 treatments crossover design will be used with 40 subjects in fasting state with a 14-day wash-out period along 4 study stages.

Planned number of subjects: 40 healthy subjects; 20 female and 20 male

Primary endpoints:

- To demonstrate bioequivalence of the fixed combination of Metformin tablets 1000 mg XR plus Gliclazide 30 mg MR compared to the co-administration of the individual tablets of Metformin 1000 mg XR and Gliclazide 30 mg MR, given as single dose to healthy volunteers in fasting state. Primary endpoints will be AUC_{0-t} , $AUC_{0-\infty}$ and C_{max} for Metformin and Gliclazide.
- To demonstrate the lack of an effect of Gliclazide on the PK of Metformin by comparing the Metformin PK following administration of the fixed combination tablet Metformin/Gliclazide and Metformin alone (AUC_{0-t} , $AUC_{0-\infty}$ and C_{max} of Metformin).
- To demonstrate the absence of an effect of Metformin on the PK of Gliclazide by comparing the Gliclazide PK following administration of the fixed combination tablet Metformin/Gliclazide and Gliclazide alone (AUC_{0-t} , $AUC_{0-\infty}$ and C_{max} of Gliclazide).

Secondary endpoints:

- The secondary endpoints variable are volume of distribution K_e , half-life elimination, clearance, and median residence time all these parameters will be presented only for informative reasons for both medications.
- To compare the **safety** and tolerability of all the experimental treatments.

Pharmacokinetic parameters:

Primary endpoints will be AUC_{0-t} , $AUC_{0-\infty}$ and C_{max} for Metformin and Gliclazide.

Other assessments: To assess clinical safety (vital signs, ECGs, lab data, physical examinations) and tolerability for all experimental treatments through adverse event report and the effect of Metformin on Gliclazide PK and vice versa.

Diagnoses and key inclusion and exclusion criteria:

Inclusion criteria:

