7.2 Rationale for Study Design

As per international clinical guidelines about Type 2 Diabetes management (Diabetes Care, 2014), Metformin, if there are no contraindications and if this is tolerated, is the drug of choice for Type 2 Diabetes. In the event Metformin monotherapy at the maximum tolerated dose does not maintain hemoglobin A1c under 7% as target for more than 3 months, then it will be necessary to add a second oral agent from another pharmacological family, such as sulphonylureas, thiazolidine, DPP4i or GLP-1-RA. Gliclazide is a second generation sulphonylurea which offers a complementary mechanism of action for Metformin.

On the other hand, there is wide experience about Metformin's and Gliclazide's association and it is particularly recommended for some clinical guidelines (Treatment Algorithm for Type 2 Diabetes, 2014) when Metformin's monotherapy is not enough to achieve treatment objectives. Therefore, a fixed dose combination has been developed as second line therapy, in cases when Metformin's monotherapy has not shown satisfactory benefit/risk.

Fixed dose combination for Metformin and Gliclazide is a generic for the existent concomitant administration of these two active ingredients which use is already generalized. Fixed dose combination has the potential advantage of making easier the therapy by reducing the number of individual dosage units to be taken by the patient. This simplifies therapy and may improve patient's compliance (Diabetes Care, 2014; Treatment Algorithm for Type 2 Diabetes, 2014.)

In case of combinations which contain the active ingredients (as proposed in this study) and with a replacement indication (i.e., use in adequately controlled patients with individual products administered simultaneously, at the same dosage level than in the combination, but in different tablets), bioequivalence should be proven between free formulations combination and marketing formulation (fixed combination) (EMA, 2009).

On the other hand, international guidelines recommend that in case of new fixed combinations, it is necessary to assess the degree which drugs affect mutually the appropriate pharmacokinetic pattern (drug - drug interaction) (EMA, 2009).

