Likewise, in Mexico, the committee to assess the marketing approval for new molecules (New Molecules' Committee) in case of new fixed dose combinations requests evidence about the lack of interaction between compounds making up the combination (drug - drug interaction) (COFEPRIS, 2013).

Clinical trial herein proposed is designed to achieve objectives stated by international guidelines as Mexico's Health Authorities in the field of bioequivalence and interactions. Although both objectives could be studied in two separate clinical trials (bioequivalence crossover design 2 x 2 and a cross interaction design 3 x 3), it is deemed more efficient to combine them in a single study. This reduces the number of subjects exposed as well as the minimization of time and costs. Therefore, the purpose of this clinical trial is mainly demonstrating bioequivalence and the drug-drug interaction of the new fixed dose combination for Metformin 1000 mg plus Gliclazide 30 mg MR compared to the concomitant dosage of individual tablets of Metformin 1000 mg XR and Gliclazide 30 mg MR. As secondary objective clinical safety and tolerability for all treatments used will be assessed.

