8.1 Investigational Drug Description

Study Sponsor will provide drugs to be administered to the subjects in each of the study visits.

- + International non-proprietary name: Metformin/Gliclazide.
- + Reference drug: Dabex[®] XR.
 - Dosage form: tablets
 - Quali-Quantitative Formula: each tablet contains 1000 mg of Metformin hydrochloride.
 - Manufacturer: Merck KGaA
 - Distributor: MERCK, S. A. de C. V.
 - Marketing Holder: MERCK, S. A. de C. V.
- + Reference drug: Diamicon MR[®].
 - Dosage form: extended release tablets
 - Quali-Quantitative Formula: Each tablet contains 30 mg of Gliclazide.
 - Manufacturer: Les Laboratoires Servier Industrie
 - Distributor: Beckman Laboratories de México, S. A. de C. V.
 - Marketing Holder: Beckman Laboratories de México, S. A. de C. V.
- + Test drug: Metformin 1000 mg/Gliclazide 30 mg MR.
 - Dosage form: tablets
 - Quali-Quantitative Formula: Each tablet contains Metformin 1000 mg/Gliclazide 30 mg MR.
 - Manufacturer: Merck, SA, Brazil.
 - Distributor: Merck, SA, Brazil.
 - Marketing Holder: Merck, SA, Brazil.
- + Dosage: Metformin 1000 mg/Gliclazide 30 mg MR.
 - Treatment 1: dosing of fixed combination of Metformin 1000 mg/Gliclazide 30 mg MR (one tablet).

Drug's name: Metformin/Gliclazide
Protocol number EMR200763-003/ BD1412-62CEC

- Treatment 2: concomitant dosing of Metformin 1000 mg/Gliclazide 30 mg (two tablet.)
- Treatment 3: dosing of Metformin 1000 mg (one tablet.)
- Treatment 4: dosing of Gliclazide 30 mg (one tablet.)

Test drug should be imported as per the following quantities and specifications:

Description: Fixed combination tablet of Metformin 1000 mg/Gliclazide 30 mg.

Quantity required for each stage of the research: 11 tablets.

60 tablets for the study.

220 tablets for the finished product analysis and dissolution profile:

60 tablets as retention sample.

Manufacturer: Merck KGaA

Products importer:

Merck S.A. de C.V.

PPD 

PPD 

Merck LATAM

PPD 

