9.6 Statistics

9.7 Sample Size

The sample size estimation is based on the CV intrasubject variability of both drugs. Because the pharmacokinetic and drug-drug interaction, evaluates changes in the bioavailability, the propose is the use the same determination for both aims.

The sample size is determined by the primary endpoint with the greatest variability under fasting conditions, AUC_{0-t} of Metformin (CV=23%). Assuming a mean treatment ratio of 0.95, and aiming at a power of 90% for the individual test, alpha=0.05 one-sided, 32 evaluable subjects are sufficient to demonstrate bioequivalence in the first step. The same arguments can be applied to the second step: Test absence of an effect of Gliclazide on the PK of Metformin, whereas the power for the third test is close to 100% with 32 subjects, due to the low variability of Gliclazide PK. Therefore, the overall power is still greater than 80% with 32 evaluable subjects. Considering a drop-out rate of approximately 20%, 40 subjects should be randomized.

According to NOM-177-SSA1-2013, this sample determination was realized with Chow & Wang (2001) equation

$$n \geq [t_{(\alpha, 2n-2)} + t_{(\beta, 2n-2)}]^2 \cdot \left(\frac{CV_{intra}}{\ln 0.8 - \ln \theta} \right)^2$$

Where:

$t(\alpha, 2n-2)$ and $t(\beta, 2n-2)$ considered the error α and β respectively

CV_{intra}: intra subject variability for crossover (or replicate crossover) study.

T_{theta}: 0.95: the target ratio in average BA between the two formulations expressed in percentage of the average reference

0.8: the least statistical power to detect (1-Power) differences between the Test and the Reference formulation (in this case the power expected is 90%)

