9.10.2 Analysis of primary and secondary endpoints

The following sequential testing of a priori ordered hypotheses will be applied, as shown below. Bioequivalence test methodology will be used in all 3 steps:

1. Test bioequivalence of fixed combination and separate tablets
2. Test absence of an effect of Gliclazide on the PK of Metformin
3. Test absence of an effect of Metformin on the PK of Gliclazide

Bioequivalence in step1:

A mixed model will be applied to log-transformed C_{max} , AUC_{0-t} and $AUC_{0-\infty}$ (both analytes) with treatment, period and sequence as fixed effects, and subject (sequence) as a random effect. Based on the residual error term 90% confidence intervals will be computed for the estimated differences Test – Reference, resulting in 90% confidence intervals for the Test/Reference ratios after back-transformation.

Drug-drug interaction in steps 2 and 3:

A mixed model will be applied to log-transformed C_{max} , AUC_{0-t} and $AUC_{0-\infty}$ (one analyte) with treatment as fixed effect, and subject as a random effect. Based on the residual error term 90% confidence intervals will be computed for the estimated differences Test – Reference, resulting in 90% confidence intervals for the Test/Reference ratios after back-transformation.

1. Bioequivalence will be concluded, if all six 90% CIs for all six primary endpoints reside within the acceptance range [0.80 – 1.25]
2. Absence of an effect of Gliclazide on the PK of Metformin will be concluded, if all three 90% CIs for Metformin endpoints reside within the range [0.80 – 1.25]
3. Absence of an effect of Metformin on the PK of Gliclazide will be concluded, if all three 90% CIs for Gliclazide endpoints reside within the range [0.80 – 1.25]

Additionally, the primary endpoints will be descriptively analyzed and graphical displays (Box-whiskers-plots) will be prepared.

Statistical model in the variance analysis of mixed effects should be applied for log-transformed parameters C_{max} , AUC_{0-t} and $AUC_{0-\infty}$ (one analyte) with TREATMENT as fixed effect and SUBJECT as randomized effect. Based on residual errors, confidence interval of 90 % will be built for estimated differences for test - reference, resulting in a confidence interval of 90 % for the test/reference ratio following transformation.

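### Steps 2 and 3 infer absence of a drug interaction from fixed combination versus single tablet, a ratio that mixes formulation with interaction and can mask an interaction

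*Protocol*

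**What the plan says.** Every sequence contains four treatments: the fixed combination (Treatment 1), co-administered single tablets (Treatment 2), metformin alone (Treatment 3) and gliclazide alone (Treatment 4).

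Protocol 5.1 makes lack of a gliclazide effect on metformin a primary objective, to be shown "by comparing the Metformin PK following administration of the fixed combination tablet Metformin/Gliclazide and Metformin alone". The third objective mirrors this for gliclazide, and hypothesis 3 in Section 6 has "Reference treatment: single administration of Gliclazide 30 mg MR". Section 9.10.2 gives the rule for step 2: "Absence of an effect of Gliclazide on the PK of Metformin will be concluded, if all three 90% CIs for Metformin endpoints" lie within 0.80–1.25. Step 3 has the same rule for gliclazide. SAP 6.1, 8 and 8.1 repeat all this, and SAP 9 declares no change. Co-administration is the reference only in step 1, the bioequivalence test.

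The purpose is worded in two ways. The Summary says: "Demonstrate the absence of drug interaction between the combination and the administration of each single tablet". Section 7.2 instead cites guidance that "it is necessary to assess the degree which drugs affect mutually the appropriate pharmacokinetic pattern (drug - drug interaction", and says the Mexican committee "requests evidence about the lack of interaction between compounds making up the combination (drug - drug interaction".

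SAP Tables 15.2.3 and 15.2.6 report co-administration against each single tablet, with 90% intervals and two one-sided tests. No hypothesis, ordered step or acceptance rule refers to them.

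**The concern.** Treatments 1 and 3 (or 1 and 4) differ in two respects: whether the partner drug is present, and which tablet is swallowed. The test tablet is a separate product. The gliclazide reference comes from another company altogether (Section 8.1, "Manufacturer: Les Laboratoires Servier Industrie"). A ratio near one may mean no interaction, or an interaction offset by a formulation difference. A ratio away from one may be formulation alone.

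Two of the three primary conclusions are therefore worded as effects of one compound on the other, although the ratio behind them does not identify such an effect. A true interaction at or just beyond the limit could be reported as absent, and a true absence could fail to be shown. Which case applies depends on F and I, which are unknown when the rule is fixed.

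**Working it through.** **Inputs from the documents.** Metformin AUC0-t within-subject CV 23%, planning ratio 0.95, one-sided alpha 0.05, 90% power per test, 32 evaluable and 40 randomized subjects, limits 0.80–1.25, steps tested in order.

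**Assumptions.** F, I, the gliclazide CV and the endpoint correlations are not in the documents. Correlations used: 0.8 between Cmax and each AUC, 0.98 between the AUCs. CVs are equal across the endpoints of an analyte.

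**1. The plan's own figure.** SD on the log scale = √ln(1 + 0.23²) = 0.2270. The sample-size formula then gives a right-hand side of 15.79, so 16 per sequence of a two-sequence crossover, or 32. (Using the raw CV gives 16.15, so 34.) Power from the two one-sided tests at 32 is 90.4%, and 32/(1 − 0.20) = 40. The stated sample size reproduces.

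**2. The identity.** T1/T3 = (T1/T2) × (T2/T3) = F × I, and likewise T1/T4 for gliclazide. If F and F × I both lie in 0.80–1.25, I is confined only to 0.80/1.25 = 0.64 through 1.25/0.80 = 1.5625. At CV 23% and n = 32, an interval passes when its point estimate is about 0.880–1.137. Passing steps 1 and 2 therefore allows an estimated I from 0.77 to 1.29.

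**3. One endpoint.** With I = 1.25, F = 0.95 and CV 23%, T1/T3 passes in 22.7% of trials, and in 17.9% together with step 1. The direct test T2/T3 passes in 5.0%.

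**4. The actual rule, metformin.** All six step 1 intervals must pass, then all three metformin intervals. Simulation used n = 32, 150,000–300,000 trials per cell and 59 residual degrees of freedom (96 observations − 32 subjects − 2 treatment − 3 period). The ranges cover gliclazide step 1 ratios of 0.90–1.00 and CVs of 10–17%. False claims at I = 1.25:

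| F | Planned (T1/T3) | Direct (T2/T3) |
|---|---|---|
| 1.05 | 0.2% | 0.9–1.2% |
| 1.00 | 1.5–1.9% | 1.5–1.9% |
| 0.98 | 3.1–4.0% | 1.7–2.1% |
| 0.97 | 4.5–5.4% | 1.7–2.1% |
| 0.95 | 7.4–9.3% | 1.7–2.2% |
| 0.90 | 14–18% | 1.6–2.1% |

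The planned rate exceeds 5% for I from 1.25 up to 1.253 (F = 0.97), 1.272 (F = 0.95) or 1.308 (F = 0.90). At F = 0.95 and I = 1.28 it is 3.9%, against 0.7% direct. Other correlations at F = 0.95 give 6.4% vs 1.2% (0.6/0.95) to 11.5% vs 2.9% (0.9/0.99). Dropping period, as the step 2–3 model does, changes nothing material.

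**5. Gliclazide.** Section 9.7 says "the power for the third test is close to 100% with 32 subjects, due to the low variability of Gliclazide PK" but gives no CV. Single-endpoint power at ratio 0.95 is 0.991 at CV 17% and 0.962 at CV 20%, so CVs up to about 17% fit that statement. With step 3 gated by steps 1 and 2, metformin F = I = 1 and gliclazide I = 1.25:

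| F | Planned, CV 17% | Planned, CV 10% | Direct |
|---|---|---|---|
| 1.00 | 2.0% | 2.0% | 2.0% |
| 0.97 | 9% | 20% | 2.0% |
| 0.95 | 20% | 49% | 2.0% |

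At F = 0.95 the rate exceeds 5% for I up to 1.291 (CV 17%) or 1.303 (CV 10%). At CV 20% and I = 1.25 it is 13%. At F = 1.05 it is at most 0.1%, against about 2% direct.

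**6. Mirror case, I = 0.80 and F = 1.05.** Metformin 8.7% vs 2.1%; gliclazide 18–46% vs 2.0%.

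**7. Power, all metformin endpoints, planned vs direct.** F = I = 1: 0.92 vs 0.92. F = 0.95, I = 1: 0.77 vs 0.83. F = I = 0.95: 0.53 vs 0.73. F = 1.05, I = 0.95: 0.83 vs 0.78.

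**The case against.** The strongest reply is that the plan defines its own question. The Summary and Section 7.1 speak of interaction between the combination and each single tablet, and Section 7.2 closes on the drug-drug interaction of the new combination. Read as total exposure from the fixed tablet against the single tablet, the planned contrast answers that question exactly. This stands, but only for that reading. Sections 5.1, 6 and 9.10.2 and SAP 8.1 conclude something else: that one compound does not affect the other.

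Second, the direct contrasts are already tabulated. SAP Table 16.1 also lists, per volunteer, both ratios whose quotient is I. The narrative on the direct tables is blacked out, so it cannot be said that they were ignored in interpretation. That is fair, and it makes the remedy cheap. It does not give those tables a role in any decision rule.

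Third, the effect is conditional. There is no inflation at F = 1.00. At F = 0.95 the metformin excess over 5% covers a narrow band of I, and 4.5–5.4% at F = 0.97 is essentially nominal. The direct rate is near 2% only because three endpoints must pass. The 49% needs CV 10%, F = 0.95 and I = 1.25 together. All of this is correct and limits the severity.

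Fourth, the direct contrast is not uniformly better: its power is lower at F = 1.05, I = 0.95. Replacing primary hypotheses after results are known would also be post hoc. Both points stand, and the fix allows for them.

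**Conclusion.** The concern holds. That the ratio cannot identify the interaction is an algebraic fact and needs no assumption. The size of the error does rest on the assumed F, I, gliclazide CV and correlations. At the planning ratio of 0.95 taken as F, with I at the upper limit, the false-claim rate is modest for metformin (7.4–9.3% vs 1.7–2.2%) and larger for gliclazide (20–49% vs 2.0% at CVs of 17–10%). With F = 1.00 there is no excess. When both effects point the same way, the planned contrast is stricter and loses power (0.53 vs 0.73 at F = I = 0.95). The step 1 bioequivalence conclusion is not affected. This should be fixed because it changes what two of the three primary steps may conclude. It does not invalidate the design or the data.

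**What to change.** **If the hypotheses can still be amended before data are seen.** In Protocol 5.1, 6 and 9.10.2 and SAP 6.1, 8 and 8.1, base the interaction conclusions on Treatment 2 vs 3 (metformin) and Treatment 2 vs 4 (gliclazide), with the same 90% interval rule. Make SAP Tables 15.2.3 and 15.2.6 the decision tables. Keep fixed combination vs single tablet as a supportive comparison of total exposure.

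**If they cannot.** The SAP text suggests this case, since Sections 12.1 and 15.2 already report findings. Keep the planned tests, but label their conclusions as formulation plus interaction. Present the Treatment 2 contrasts as the interaction evidence, marked as outside the pre-specified rule. Do not claim absence of interaction from the fixed-combination contrast alone.

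**Cost.** The second route is wording in the report. The first is an amendment to two primary hypotheses, with committee approval if substantial (Protocol 11.5). Neither needs new subjects, samples, assays or tables. The price of the first is some power when the effects oppose within the limits: 0.78 instead of 0.83 for all metformin endpoints at F = 1.05, I = 0.95.
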